Retrospective Evaluation of the Clinical and Radiographic Performance of coflex® Interlaminar Technology Versus Decompression With or Without Fusion.

Study ID Number: CRDC2016

Version 5.0

02November2016

Study Phase: Post-Market

Paradigm Spine

[name]

[name]

Change History

Version	Version Date	Summary of Changes
1.0	14June2016	Original
2.0	28June2016	Data collection to include 1 or 2 level decompression with or without fusion.
3.0	11July2016	Protocol title to reflect evaluation of coflex versus efficacy.
4.0	19August2016	Study Start Date and End Date applicable for Baptist IRB
5.0	22Novmeber2016	Data collection to include 5000 patients from 50 sites. Primary and Secondary Endpoints.

Table of Contents

Retrospective Evaluation of the Clinical and Radiographic Performance of coflex® Interlaminar Technology Versus Decompression With or Without Fusion.....	1
Table of Contents.....	2
Investigator Signature Page.....	3
Protocol Summary	4
Retrospective Evaluation of the Clinical and Radiographic Performance of coflex® Interlaminar Technology Versus Decompression With or Without Fusion.....	4
Study Abbreviations	5
1.0 Introduction	6
2.0 Study Purpose.....	6
2.1 Primary Objective	6
2.2 Secondary Objectives	6
3.0 Eligibility Criteria.....	7
3.1 Inclusion criteria.....	7
3.2 Exclusion criteria	7
4.0 Study Design	7
4.1 Endpoints	7
4.2 Data Collection Summary	8
4.3 Informed Consent	9
4.4 Data Collection Procedures	9
4.4.1 Baseline Visit	9
4.4.2 Surgical Treatment Visit.....	10
4.4.3 Post-Operative Hospital Stay	11
4.4.4 Follow-Up Visits	11
5.0 Statistical Analysis.....	11
5.1 General Information	11
5.2 Primary Endpoint	12
5.3 Secondary Endpoints.....	12
6.0 Study Management	12
6.1 Ethics.....	12
6.2 Data Entry	12

Investigator Signature Page

My signature below attests that I have read the contents of this protocol and agree to conduct the study according to the protocol and that the study will not be initiated without the approval of the appropriate Institutional Review Board or Independent Ethics Committee.

Investigator:

Print Name:

Signature:

Date:

Protocol Summary

Study Title	Retrospective Evaluation of the Clinical and Radiographic Performance of coflex® Interlaminar Technology Versus Decompression With or Without Fusion.
Purpose	To evaluate clinical, radiologic and patient-reported outcomes who have been treated 1 or 2 levels with the coflex® Interlaminar Technology or decompression with or without fusion.
Study Design	Retrospective, multi-center, post-market clinical study
Devices	coflex® Interlaminar Technology
Data Collection	Clinical, radiologic and patient reported outcomes data will be collected for approximately 5000 patients from 50 sites
Study Duration	Up to 6 months for data collection Start Date: June 2013 End Date: April 2017
Study Objectives	
Primary Objective:
 
• To assess the operative details and safety outcomes associated with the use of the coflex device• To assess post-operative adverse events• To assess post-operative follow-up duration 
Secondary Objectives:
 
• To measure and compare patient reported outcomes (e.g., VAS, Patient Satisfaction and ODI) at baseline and final follow-up• To measure and compare clinical and radiologic outcomes at baseline and final follow-up• To measure and compare the clinical, radiologic, and patient reported outcomes at interim follow-up visits• To assess the impact of demographics and risk factors on clinical, radiologic, and patient reported outcomes•
Inclusion Criteria	Patients must meet the criteria specified in the device labeling including radiographic confirmation of at least moderate lumbar stenosis, which narrows the central spinal canal at one or two contiguous levels from L1-L5 that require surgical decompression.
Exclusion Criteria	There are no exclusion criteria's for this study.

Risk/Benefit Assessment

The study is a retrospective analysis of medical records that poses no risk to the patients and minimal risk to loss of patient privacy. All results will be de-identified in the process of data review. There are no benefits to the subject as this data is being collected to obtain additional clinical evidence to support publications and marketing.

Study Abbreviations

Abbreviation	Definition
BMI	Body Mass Index
FDA	Food and Drug Administration
GCP	Good Clinical Practice
HIPAA	Health Insurance Portability and Accountability Act of 1996
ICH	International Committee on Harmonization
IRB	Institutional Review Board
MRI	Magnetic Resonance Imaging
CT	Computed Tomography
DEXA	Dual Energy X-ray Absorptiometry

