3.0 Eligibility Criteria

3.1 Inclusion criteria

Patient considered for enrollment in this study must meet all of the following inclusion criteria:

- Patients must meet the criteria specified in the device labeling including radiographic confirmation of at least moderate lumbar stenosis, which narrows the central spinal canal at one or two contiguous levels from L1-L5 that require surgical decompression.

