4.0 Study Design

This is a retrospective, multi-center, post-market study collecting clinical, radiographic, and patient reported outcomes for subjects who have been treated 1 or 2 levels with the coflex® Interlaminar Technology or decompression with or without fusion.

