5.2 Primary Endpoint

Overall duration of follow-up care and incidence of secondary surgical interventions will be analyzed to evaluate overall effectiveness of the use of the coflex® Interlaminar Technology

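### The plan does not say what June 2013 to April 2017 bounds and sets no common surgery window or record cut-off, although both Section 5.2 endpoints grow with the time available

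*Combined protocol and SAP*

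**What the plan says.** - **Time frame.** The only statement is the Study Duration row of the Protocol Summary: "Up to 6 months for data collection Start Date: June 2013 End Date: April 2017". No other section explains the two dates. As context only, the change history describes the version 4.0 change as "Study Start Date and End Date applicable for Baptist IRB".
- **Procedures.** Section 4.0 covers subjects "treated 1 or 2 levels with the coflex® Interlaminar Technology or decompression with or without fusion", so there are three groups.
- **Eligibility.** Section 3.1 has one criterion, which begins "Patients must meet the criteria specified in the device labeling including radiographic confirmation of at least moderate lumbar stenosis". It contains no surgery date. Section 3.2 states that nothing is excluded, so no minimum follow-up applies either.
- **Follow-up.** Section 4.4.4 takes every clinic visit up to the last one in the chart, with no fixed horizon.
- **Endpoints.** Section 5.2: "Overall duration of follow-up care and incidence of secondary surgical interventions will be analyzed to evaluate overall effectiveness" of coflex use. Section 4.1 separately ties patient-reported outcomes to the primary objective, so the point made here concerns the Section 5.2 endpoints only.
- **Analysis.** Section 5.1 plans t-tests against baseline for continuous outcomes and Fisher's exact test for categorical ones, at 0.05. Section 5.3 lists age, ethnicity, race, workers' compensation, smoking status and gender for the association analysis. Surgery date is not among them, although Section 4.4.2 collects it.

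**The concern.** Time under observation cannot exceed the record cut-off minus the surgery date, and the crude proportion with a second operation rises with time observed. Both Section 5.2 endpoints therefore carry the surgery date inside them. If one procedure was done more recently than another at the participating sites, its patients will show shorter follow-up and fewer reoperations even when the underlying hazard is the same.

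Nothing in the plan prevents or corrects this. Two abstractors could also assemble different cohorts from the same charts, because the documents do not say which surgery dates qualify. At stake is whether a difference on either endpoint could be attributed to the procedure, in a study whose stated purpose is to support publications and marketing.

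**Working it through.** **1. The dates.** June 2013 to April 2017 is 46 months (47 if both end months count). The title page dates version 5.0 "02November2016"; the change history gives 22 November 2016. From those dates to April 2017 is 4.3 months (22 November to 1 April) to 5.9 months (2 November to 30 April). This fits an abstraction period of up to 6 months.

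**2. There is no planned figure to reproduce.** The plan gives about 5000 patients and 50 sites, with no reoperation rate, allocation or power calculation. Everything below is an illustration with assumed inputs: a constant reoperation hazard *h*, identical in both groups; the dates taken to bound surgeries; and one cut-off in April 2017.

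**3. Effect of surgery date for single patients.** Incidence by time *t* is 1 − exp(−*ht*). Compare 1 year with 46/12 = 3.83 years:

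| *h* per year | 1 year | 3.83 years |
|---|---|---|
| 2% | 2.0% | 7.4% |
| 3% | 3.0% | 10.9% |
| 5% | 4.9% | 17.4% |

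**4. Effect for groups.** If surgeries are spread evenly over the *T* years before the cut-off, mean available follow-up is *T*/2 and crude incidence is 1 − (1 − exp(−*hT*))/(*hT*).

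At *h* = 5%:
- 46 months: *hT* = 0.1917, incidence 9.0%, mean available follow-up 46/2 = 23 months.
- 24 months: *hT* = 0.10, incidence 4.8%, mean available follow-up 24/2 = 12 months.

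At 3% per year the pair is 5.5% and 2.9%; at 8% it is 13.9% and 7.6%.

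With an assumed 2500 per group, 9.00% against 4.84% gives z = 0.0416/√(2 × 0.0692 × 0.9308/2500) = 5.8. The 24-month spread is itself an assumption. Keeping 5% and 2500 per group, a spread of 36 months against 46 gives z = 2.4, and 40 against 46 gives z = 1.4.

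**5. Which part of the plan produces this.** Simulation with no treatment effect: 1000 runs per setting, 1667 per group (equal thirds of 5000, assumed), *h* = 2%, 3% and 5%. Entries are the share of runs significant at two-sided 0.05, as the range over the three hazards.

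| Surgery dates in the two groups | Fisher's exact | Person-time rate comparison |
|---|---|---|
| Same spread | 3.4% to 5.7% | 4.5% to 6.7% |
| Mild difference (mean 1.92 vs 1.44 years available) | 29% to 59% | 4.6% to 5.7% |
| Earlier vs later half of the 46 months | 100% | 3.7% to 5.3% |

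Accounting for time at risk removes the false positives for secondary surgery. In the mild and the half-window settings all surgeries already lie inside one window with one cut-off, so a common window alone would not cure the problem.

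**The case against.** **A reader might infer that the row contradicts itself, 6 months against 46.** The documents do not support that. In a chart review the abstraction period and the record period are different quantities. The 6 months is labelled as data collection, and it fits the interval from version 5.0 to April 2017. The change history suggests that the dates may even belong to one site's IRB. The dates are undefined; they are not shown to be in conflict.

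**A reader might infer that the plan commits to a flawed test between procedures.** It does not. Section 5.2 speaks of coflex use, Section 5.1 compares continuous outcomes with baseline, and its Fisher comparison names no groups. The bias arises only when procedures are compared. The title says versus and comparator patients are collected, so a comparison is foreseeable, but no specific test is planned.

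**A reader might take z = 5.8 as the expected bias here.** It rests on an assumed hazard, an assumed later uptake of coflex and two assumed groups of 2500 where the plan has three procedures. It measures crude incidence under unequal follow-up. No calendar-time effect beyond that has been quantified. Likewise, 23 against 12 months is time available, which is a ceiling; follow-up care may end well before any cut-off.

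**Strict comparison within site and year would be too sparse.** This is correct. 5000/50 = 100 patients per site, and over three procedures and five calendar years that is 100/15, or about 7 per cell. No section says that every site performs all three procedures.

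What survives is that there is no surgery window, no minimum follow-up, no cut-off and no analysis that uses time at risk.

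**Conclusion.** The concern holds as a gap in definition and analysis. The plan leaves June 2013 to April 2017 unexplained and sets no index-surgery window or record cut-off common to the three procedures. Its Section 5.2 endpoints both depend on time available, and its stated tests ignore it.

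The size depends on how far surgery dates differ between procedures, which the documents do not tell. Under the assumptions shown, equal hazards can give 9.0% against 4.8%, and a mild difference in dates can raise the false-positive rate of Fisher's exact test to between 29% and 59%. A small difference (40 against 46 months) matters much less, and with identical surgery-date distributions there is no problem of this kind.

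For secondary surgery the remedy is mainly the analysis method. For follow-up duration, and for any change in practice over calendar time, the dates and an adjustment are needed as well. The plan should be corrected before any comparison between procedures is made.

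**What to change.** 1. **Study Duration row.** Replace it with three labelled items: the index-surgery window, the same for all three procedures; one record cut-off date; and the chart-abstraction period of up to 6 months. If any date applies to one IRB only, say so.
2. **Section 3.1.** Add the index-surgery window as an inclusion criterion.
3. **Section 5.2, secondary surgery.** Analyse as time to event from the date of surgery, censored at the earlier of last contact and the cut-off. This is safer than a simple person-time rate, which is right only if the hazard is constant.
4. **Section 5.2, comparisons between procedures.** Adjust both endpoints for calendar time of surgery, with site as a stratum or random effect and no site-by-year cells. With site as a stratum, sites that contribute only one procedure add nothing to the comparison; a random effect keeps them but leans on differences between sites.
5. **Section 5.2, follow-up duration.** Report it relative to the time available to the cut-off, and do not read it as effectiveness unadjusted.

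**Cost.** Charts outside the window are lost and the analysis is slightly more complex. No new variable is needed for the time scale, because date of surgery and follow-up visits are already collected.

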1.0 Introduction

The coflex® Interlaminar Technology - manufactured by Paradigm Spine - is intended for use as a permanent implant between the lamina of 1 or 2 lumbar motion segments in the treatment of moderate to severe lumbar spinal stenosis. The device is specifically designed to provide stabilization without fusion in cases of stenosis with or without facet joint hypertrophy, subarticular recess stenosis or foraminal stenosis. It is restricted for use to one or two levels in the region of L1 – L5.

The height of the neuroforamen is maintained and the facet joints will be relieved. By this a further destruction is prevented. Unlike conventional stabilization methods as for example spinal fusion, the function of the segment will be maintained and adjacent structures will be effectively protected.

Possible risks, which could occur after implantation of the coflex® Interlaminar Technology are breakage of the implant, displacement of the implant, pain which is caused by the implant, infections, bleedings and hematoma. The benefit of the study lies in the fact that first-time retrospective data is raised for potential improvement regarding therapy of lumbar back pain with the treatment of the lumbar spinal stenosis, which, in the future, can lead to an improvement of the therapy.

In this study, Paradigm Spine will retrospectively collect clinical and radiographic data for patients treated with the coflex® Interlaminar Technology during normal conditions of use. This data will provide evidence to support publications and marketing.

2.0 Study Purpose

2.1 Primary Objective

- To assess the operative details and safety outcomes associated with the use of the coflex device
- To assess post-operative adverse events
- To assess post-operative follow-up duration

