4.4.2 Surgical Treatment Visit

- Operative Summary
 - Date of surgery
 - Surgical procedure
 - Operative time
 - Estimated blood loss
 - Anesthesia details
 - Treated level(s)
 - Device size
 - Intra-operative/early post-operative complications, such as:
 - Dural tears
 - Hematomas
 - Fractures
 - Nerve injury
 - Diagnostic imaging History
 - Dictated operative notes
- Repeat Surgery Summary
 - Date of surgery
 - Reason for surgery (reoperation, revision, removal, etc.)
 - Surgical procedure
 - Operative time
 - Estimated blood loss
 - Anesthesia details
 - Treated level(s)
 - Surgical intervention performed
 - Device size
 - Intra-operative/early post-operative complications

- Dural tears
- Hematomas
- Fractures
- Nerve injury
- Diagnostic imaging History

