4.4.4 Follow-Up Visits

The following longitudinal data will be collected for all follow-up clinic visits through final follow-up:

- Work status / ADL
- Compliance with postoperative protocol/restrictions (if applicable)
- VAS (as available)
- ODI (as available)
- Patient satisfaction (as available)
- Complications
- Secondary treatments
- Narcotics use
- Diagnostic Imaging
- Incidence of Epidural Steroid Injections (ESI)

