5.0 Statistical Analysis

5.1 General Information

All continuous outcome measurements at follow-up time points will be compared to baseline values using a t-test for superiority. Categorical outcome measurements will be compared using a Fisher's exact test for superiority. Statistical significance for these analyses will be demonstrated with a p-value less than 0.05.

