5.3 Secondary Endpoints

The clinical outcomes will be summarized; however, since the collection of these measures is not standard of care, this data will only be collected as available. In addition, data will be used to analyze the association between coflex® Interlaminar Technology use and outcomes with age, ethnicity, race, workers' compensation, smoking status, and gender. New and/or worsening complications will be summarized.

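### Duration of follow-up care is used to judge coflex effectiveness, but the protocol specifies no status at last contact, follow-up visit date or vital status, so different endings are pooled

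*Combined protocol and SAP*

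**What the plan says.** Section 2.1 lists as a primary objective "To assess post-operative follow-up duration". Section 5.2 goes further: "Overall duration of follow-up care and incidence of secondary surgical interventions will be analyzed to evaluate overall effectiveness" of coflex. It does not say whether a longer or a shorter duration is favourable, or which event closes the interval.

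The start of the interval is available, because section 4.4.2 lists "Date of surgery". For the end, section 4.4.4 says "The following longitudinal data will be collected for all follow-up clinic visits through final follow-up", but final follow-up is not defined. The list that follows has ten items: work status/ADL, compliance, VAS, ODI, satisfaction, complications, secondary treatments, narcotics, imaging and epidural steroid injections. A visit date is listed for baseline (4.4.1) but not for follow-up.

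Section 5.1 gives one method for continuous outcomes: "All continuous outcome measurements at follow-up time points will be compared to baseline values using a t-test for superiority". Section 5.3 adds "New and/or worsening complications will be summarized". The Protocol Summary gives "Start Date: June 2013 End Date: April 2017" as the study dates.

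**The concern.** A duration of care can be read as effectiveness only if one knows what ended it. Take four patients whose last chart entry is three months after surgery. One was discharged well, one moved to another surgeon, one died, and one was still in treatment when the chart was read. On the listed items, each contributes three months to the endpoint.

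The direction of the endpoint is therefore undetermined. A procedure after which patients recover quickly and one after which they go elsewhere can show the same short duration. Two procedures with equal care needs can also show different durations because one set of sites keeps its patients better. The protocol says that the data are meant to support publications and marketing, so a raw duration could be reported as evidence of benefit.

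Deaths are a second, smaller gap. Safety outcomes are a primary objective, but no word for death appears in the protocol. A death not regarded as a complication could be recorded as an ordinary end of follow-up.

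**Working it through.** **Check of the text.** I looked in each data list for three items: the reason follow-up ended, the date of last contact, and vital status.

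| Place | Reason for ending | Date of last contact | Vital status |
|---|---|---|---|
| 4.1 Endpoints | no | no | no |
| 4.2, Table 1 (ten rows) | no | no | no |
| 4.4.1 Baseline | no | baseline visit date only | no |
| 4.4.2 Surgery | no | dates of index and repeat surgery only | no |
| 4.4.3 Hospital stay | no | length of hospital stay only | no |
| 4.4.4 Follow-up | no | no | no |

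Length of hospital stay concerns discharge from hospital, not discharge from the surgeon's care, so it does not close the interval. Sections 5.1 to 5.3 contain no censoring rule, competing-event rule or time-to-event method. The t-test in 5.1 compares with baseline, and duration has no baseline value.

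**Size.** The plan states no figure for duration, loss or death, so there is nothing to reproduce. Both illustrations below rest on assumed inputs.

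*Constant rates.* Let the mean recorded duration be 12 months in each group, so the total rate of ending is 1/12 = 0.0833 per month. If a share p of endings are discharges and the rest are losses, the discharge rate is p/12 and the mean time to discharge is 12/p.

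- p = 80%: 12/0.8 = 15 months
- p = 70%: 12/0.7 = 17.1 months
- p = 50%: 12/0.5 = 24 months

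The recorded difference is zero throughout. The hidden difference is 15 − 15 = 0 months at 80% v 80%, 17.1 − 15 = 2.1 at 80% v 70%, and 24 − 15 = 9 at 80% v 50%.

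*Simulation including death and a data cut.* Recorded duration is the smallest of time to discharge, loss, death and data cut. Assumptions: surgery dates spread evenly over the 46 months from June 2013 to April 2017, exponential times, 2% deaths per year, and a true median time to discharge of 12 months.

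| Loss per year | Median recorded duration (months) | Share ending in discharge |
|---|---|---|
| 0% | 8.3 | 64% |
| 10% | 7.5 | 59% |
| 30% | 6.2 | 49% |

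Care needs are the same in all three rows. The recorded median falls by 8.3 − 6.2 = 2.1 months through loss alone. Even with no loss it lies below 12, mainly because 34% of patients are still under care at the cut.

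**Check of the remedy.** Censoring every undocumented ending is not safe. Take two identical groups with a true discharge share of 80% and the same 12-month mean. If one documents all its discharges and the other half of them, the documented shares are 80% and 40%. The estimates are then 12/0.8 = 15 and 12/0.4 = 30 months, a spurious gap of 15 months. Counting the undocumented endings as discharges at last contact returns the second group to 15. If those endings were really losses, that coding would make time to discharge look too short. Both codings are needed.

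**The case against.** Five objections carry weight.

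First, a reader might infer that nobody will record how follow-up ended. The documents do not support that. The case report form is not included, and section 4.1 describes its own list as non-exhaustive. A visit date, in particular, may well be on the form. What stands is that a primary endpoint depends on items the protocol does not specify.

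Second, a reader might infer that deaths will go uncollected. Adverse events are a primary objective, and complications are gathered at surgery, during the hospital stay and at follow-up. A treatment-related death would probably surface there. Deaths from other causes need not, and a surgeon's chart may not hold all of them even with a new field.

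Third, other follow-up items (narcotics use, secondary treatments, work status and, where available, VAS and ODI) partly separate a patient who is well from one still in treatment. That is true, but they do not identify loss, transfer or death.

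Fourth, the objective in 2.1 could mean only the length of available observation, for which every kind of ending validly counts. That reading is reasonable for 2.1 alone. It does not fit 5.2, where duration is a measure of effectiveness. Time to discharge is still one possible definition, not the one the protocol states.

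Fifth, section 5.2 describes no comparison of duration between procedures. The two-group figures show what would happen if one were made, as the study title suggests.

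**Conclusion.** The concern holds as a gap in the specification of a primary endpoint. Following the plan as written pools discharge, loss or transfer, death and continuing care into one duration, and that duration cannot be read as effectiveness in either direction.

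The size is unknown. Under assumed constant rates and an assumed 12-month mean, the hidden difference runs from 0 to 9 months over the splits shown. It is 0 when the mix of endings is the same in both groups. The 9-month figure is not an estimate for this study. The documents give no basis for choosing a split, or for saying that coflex would be favoured or disfavoured.

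This should be corrected before chart abstraction is complete.

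**What to change.** Add to section 4.4.4 and Table 1 the date of last contact and the status at last contact: discharged, still under care at extraction, transferred or lost, died, or not documented.

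In section 5.2, report the split of endings by procedure, and state that raw duration will not be interpreted as effectiveness. If duration of care is kept as an effectiveness endpoint, define it as time from surgery to documented discharge. Censor patients still under care and those transferred or lost, and treat death as a competing event. Analyse undocumented endings twice, once as censored and once as discharged at last contact, and show both results. Censoring the transferred or lost assumes that leaving is unrelated to recovery, so the split of endings should be presented beside the estimate.

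Report all deaths found in the charts with the safety outcomes.

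The cost is one more dated item abstracted from charts already being read, wording in 5.2 and, if the endpoint is kept, a competing-risk analysis. Some charts will not give the reason, and the sensitivity analyses will then show a wide range. Adding the item later would mean reopening charts at up to 50 sites after a collection period of up to 6 months.
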